## 6 Treatment

### 6.1 Study treatment

For this study, the term “investigational treatment” or “study drug” refers to INC280. The dose and treatment schedule are listed in [Table 6-1](#).

The orally administered film-coated tablet formulation will be provided in up to three strengths of 100 mg, 150 mg and 200 mg (if available) free base equivalent. For the list of excipients, please refer to current [Investigator’s Brochure].

#### 6.1.1 Dosing regimen

INC280 tablet will be administered orally on a continuous twice daily (BID) dosing schedule, on a flat scale of mg/day and not individually adjusted by weight or body surface area. A complete cycle of treatment is defined as 21 days of twice daily treatment with INC280. The investigator must instruct the patient to take the study drug exactly as prescribed.

- Except on days of PK sampling, patients should take 400 mg INC280 tablets twice daily (BID) at approximately the same time each day starting at Cycle 1 Day 1.
- Each dose of INC280 is to be taken with a glass of water (at least 8 ounces – approximately 250 mL) and consumed over as short a time as possible (i.e., not slower than 1 tablet every 2 minutes).
- Patients should be instructed to swallow the tablets whole and not to chew them.
- INC280 should be administered in the fasted state, at least 1 hour before or 2 hours after a meal. The morning and the evening doses should be taken 12 ( $\pm$  4) hours apart, although 12-hour interval is highly recommended. The morning dose should be taken the same time each morning. If a dose is not taken within 4 hours of the planned dosing time, the missed dose should not be replaced
- Only for Cohort 6 and 7, INC280 can be administered with or without food.
- On days when PK blood samples are to be collected, patients will be instructed to hold their dose until arrival at the study center. INC280 will be administered at the site in the morning prior to the PK blood draws supervised by a member of the research team. The exact time of drug administration should be recorded in the appropriate eCRF. If a patient vomits within 4 hours of INC280 dosing, the time of vomiting should be recorded on the eCRF.
- Patients should be instructed not to make up for missed doses or partial doses (i.e., when the entire dose is not taken as instructed). A missed or partial dose will be defined as a case when the full dose is not taken within 4 hours of the scheduled twice daily dosing. If that occurs, then the dose (or part remaining dose) should not be taken and dosing should restart with the next scheduled dose. If vomiting occurs, no attempt should be made to replace the vomited dose before the next scheduled dose.
- During the whole duration of treatment with INC280, the patient is recommended to use precautionary measures against ultraviolet exposure (e.g., use of sunscreen, protective clothing, avoid sunbathing or using a solarium).

The investigator should instruct the patient to take INC280 exactly as prescribed. All dosages prescribed and dispensed to the patient and all dose changes during the study must be recorded on the Dosage Administration Record eCRF.

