**Table 7-5      ECG collection plan for approximately 30 enrolled patients at selected sites**

Cycle	Day	Time	ECG Type	Number of ECGs
Screening		Anytime	12 Lead	3

Cycle	Day	Time	ECG Type	Number of ECGs
1	1	Pre-dose Post-dose 1 h (within 15 min prior to PK) Post-dose 2 h (within 15 min prior to PK) Post-dose 4 h (within 15 min prior to PK) Post-dose 8 h (within 15 min prior to PK)	12 Lead	3
1	15	Pre-dose Post-dose 1 h (within 15 min prior to PK) Post-dose 2 h (within 15 min prior to PK) Post-dose 4 h (within 15 min prior to PK) Post-dose 8 h (within 15 min prior to PK)	12 Lead	3
3	1	Pre-dose (within 15 min prior to PK)	12 Lead	3
EOT		Anytime	12 Lead	3
Unscheduled ECG		Anytime if clinically indicated	12 Lead	3

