**Table 7-6 ECG collection plan for remaining patients, including patients in Cohort 6 and Cohort 7**

Cycle	Day	Time	ECG Type	Number of ECGs
Screening		Anytime	12 Lead	3
1	1	Pre-dose	12 Lead	3
1	15	Post-dose 2 h (within 15 min prior to PK)	12 Lead	3
3	1	Pre-dose	12 Lead	3
EOT		Anytime	12 Lead	3
Unscheduled ECG		Anytime if clinically indicated	12 Lead	3

Baseline is defined as the pre-dose assessment on Cycle 1 Day 1 before study drug administration.

All ECG assessments will be performed in the supine position. Detailed instructions regarding the ECG collection will be provided to the investigators in a separate manual prior to the start of the study. INC280 pharmacokinetic evaluation will be conducted in parallel to cardiac evaluations (see [Section 7.2.3](#)). All ECGs should be performed within 15 minutes prior to the collection of PK sample. The triplicate ECGs should be taken approximately 2-4 minutes apart. An ECG may be repeated at the discretion of the investigator at any time during the study and as clinically indicated.

All ECGs recorded for each time point will be transmitted electronically to a central laboratory and will be centrally reviewed by an independent reviewer. Any original ECG not transmitted electronically to the central laboratory should be forwarded for central review. Review of all ECGs from a particular patient should be performed by a single reader. The ECG lead for interval duration measurements should be pre-specified. Baseline and all subsequent ECGs should be based on the same lead.

Interpretation of the tracing must be made by a qualified physician. Each ECG tracing should be labeled with the study number, patient initials (where regulations permit), patient number, ECG nominal day and time, ECG actual date and time (using a 24-hour clock, record up to second), ECG replicate number, measured variables (QT, RR, PR, QRS), derived variables

(QTcB, QTcF, and HR), ECG lead date, and kept in the source documents at the study site. Clinically significant abnormalities present when the patient signed informed consent should be reported on the Medical History eCRF page. Clinically significant findings must be discussed with Novartis prior to enrolling the patient in the study. New or worsened clinically significant findings occurring after informed consent must be recorded on the Adverse Events eCRF page.

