**Table 7-7 Pharmacokinetic blood collection log for approximately 30 enrolled patients at selected sites**

Cycle	Day	Scheduled Time Point	Dose Reference ID	PK Sample No	Sample Volume (mL)
1	1	Pre-dose/0h	1	1	3
1	1	Post-dose 0.5h ( $\pm$ 5min)	1	2	3
1	1	Post-dose 1h ( $\pm$ 10min)	1	3	3
1	1	Post-dose 2h ( $\pm$ 10min)	1	4	3
1	1	Post-dose 4h ( $\pm$ 20min)	1	5	3
1	1	Post-dose 6h ( $\pm$ 20min)	1	6	3
1	1	Post-dose 8h ( $\pm$ 20min)	1	7	3
1	15	Pre-dose/0h	2	201 a	3
1	15	Post-dose 0.5h ( $\pm$ 5min)	2	9	3
1	15	Post-dose 1h ( $\pm$ 10min)	2	10	3
1	15	Post-dose 2h ( $\pm$ 10min)	2	11	3
1	15	Post-dose 4h ( $\pm$ 20min)	2	12	3
1	15	Post-dose 6h ( $\pm$ 20min)	2	13	3
1	15	Post-dose 8h ( $\pm$ 20min)	2	14	3
3	1	Pre-dose/0h	3	301 a	3

Cycle	Day	Scheduled Time Point	Dose Reference ID	PK Sample No	Sample Volume (mL)
Unscheduled		Anytime		1001+	3
		Total scheduled			45

aDose reference IDs with three digits refer to the dose administered and dosing time of the last dose prior to collection of the corresponding PK sample

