4.7.2 Baseline

As defined in [Section 2.8.2](#), the last available assessment before or on the date of start of study drug is defined as “baseline” value or “baseline” assessment.

Laboratory data

If both central and local laboratory assessments were performed on the same date and corresponding to the baseline assessment date, then the central laboratory assessment will be used for the calculation of baseline.

If labs with duplicate laboratory measurements taken at the last assessment date on or before the start date of study treatment from the same sources (both from local or central), then the rule described below will be applied for the calculation of baseline.

- For gradable labs, the value of lower CTCAE grade will be considered as the baseline value. If several records have the same absolute grade, but in different directions, 2 baselines should be created, the record with grade below 0 should be the baseline of the 'Hypo' parameter, and the other record should be the baseline for the 'Hyper' parameters.
- For non-gradable labs:
 - If both within normal range: take average value
 - If one within normal range and the other outside: take the one within normal range
 - If both outside normal range: take the one closest to the normal range

ECGs

Baseline for ECG measurement is the average of the pre-dose replicate measurements on the baseline day. Unscheduled assessments will not be included in the calculation of the average. Study day 1 scheduled pre-dose ECGs will be considered to have been obtained prior to study drug administration if dosing time or ECG time is missing.

If a scheduled pre-dose measurement actually occurred post-dose, then the corresponding measurement will be treated and analyzed similar to an unscheduled post-dose measurement. For unscheduled assessments on study day 1, the assessment is classified as post-baseline.

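### On PK days, Protocol Section 6.1.1 puts the on-site dose before the blood draws, which contradicts the pre-dose samples required by Tables 7-7 and 7-8, most plainly on Cycle 3 Day 1

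*Protocol*

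**What the plan says.** Protocol Section 6.1.1 covers PK days in one bullet. First, "patients will be instructed to hold their dose until arrival at the study center". Then, "INC280 will be administered at the site in the morning prior to the PK blood draws supervised by a member of the research team". Sites record on the eCRF when the dose was given. The bullet does not distinguish pre-dose from post-dose draws.

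Protocol Section 7.2.3 refers to Tables 7-7 (full schedule, about 30 patients) and 7-8 (sparse schedule, remaining patients including Cohorts 6 and 7) for the sampling times. Both tables list a pre-dose/0h sample on Cycle 1 Day 1, Cycle 1 Day 15 and Cycle 3 Day 1. On Cycle 3 Day 1 nothing else is scheduled. A footnote to each table ties the Day 15 and Cycle 3 pre-dose samples to the "dosing time of the last dose prior to collection of the corresponding PK sample".

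Three other provisions bear on the point:

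- Protocol Section 7.1 requires Cycle 1 Day 1 assessments to precede the first dose unless stated otherwise.
- Protocol Section 7.2.3 requires the actual draw time and the time of the last prior dose to be recorded on all sampling days.
- SAP Section 2.1 says that no PK analysis is included in the planned report, and SAP Section 2.8.4 marks pharmacokinetics as not applicable.

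**The concern.** The dosing section and the sampling tables give opposite orders for the same morning. Section 6.1.1 is where a site looks for how to give the drug, and it puts the dose first. The tables put a sample first on every PK day.

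At stake is the trough concentration. Characterising the pharmacokinetics of INC280 and its metabolite is secondary objective 5 in Table 3-1. Section 10.5.4 summarises concentrations by visit, and Table 10-1 lists exposure over the dosing interval and the accumulation ratio. Tablet Tmax is 1 to 2 hours (Section 1.2.1.2.4), so concentrations rise soon after a dose. A sample drawn in that window but labelled 0h would overstate the trough. Section 10.1.4 names only vomiting within 4 hours of the dose as making a PK sample non-evaluable, so it does not itself exclude a mistimed pre-dose sample. The definition of an evaluable profile is left to the analysis plan.

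**Working it through.** **Reproducing the tables' own totals.** Each sample is 3 mL.

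- Full schedule (Table 7-7): 7 samples on Cycle 1 Day 1, 7 on Cycle 1 Day 15 and 1 on Cycle 3 Day 1, which makes 15. 15 × 3 = 45 mL, as stated.
- Sparse schedule (Table 7-8): 2 + 2 + 1 = 5 samples. 5 × 3 = 15 mL, as stated.

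Both totals are reached only if the three pre-dose samples are counted, so those rows belong to the planned schedule.

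**The two instructions side by side.**

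| PK day | Section 6.1.1 | Tables 7-7 and 7-8 | Can both be followed? |
|---|---|---|---|
| Cycle 1 Day 1 | dose, then draws | pre-dose sample, then post-dose samples | only if 6.1.1 is read as meaning the post-dose draws; Section 7.1 also puts assessments before the first dose |
| Cycle 1 Day 15 | dose, then draws | pre-dose sample, then post-dose samples | only on the same reading; no other text settles it |
| Cycle 3 Day 1 | dose, then draws | pre-dose sample only | no; there is no post-dose draw for the dose to precede |

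**Which samples are exposed.** Three samples per schedule are labelled pre-dose. The Cycle 1 Day 1 sample comes before any drug, so it is not a trough, and Section 7.1 protects it. That leaves Day 15 and Cycle 3. Read with their pre-dose label, the footnote ties them to the preceding dose and not to that morning's dose, so they are meant as troughs.

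- Full schedule: 2 of 15 samples (13%).
- Sparse schedule: 2 of 5 samples (40%). Section 7.2.3 assigns this schedule to the majority of patients.

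If 6.1.1 were followed literally on every PK day, Cycle 1 Day 1 included, the samples obtainable as scheduled would be 15 − 3 = 12 (36 mL) on the full schedule and 5 − 3 = 2 (6 mL) on the sparse one, with none on Cycle 3 Day 1. That is the outer bound. With Cycle 1 Day 1 protected, the figures are 13 of 15 and 3 of 5.

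**The case against.** The best defence is that the intention is clear. The table rows are labelled pre-dose, Section 7.2.3 makes the tables the source for sampling times, and the home dose is held until arrival, which fits a pre-dose draw. A careful site would follow the tables. Actual dose and draw times are both recorded, so a mistimed sample can be identified. Most of this stands, and it makes mistiming a possibility and not an expected result. It does not remove the contradiction. Holding the home dose fits either order, because the post-dose samples also need a supervised, timed dose. On Cycle 3 Day 1 no reading satisfies both texts.

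Three stronger readings are tempting, and the documents do not support them.

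- **That 6.1.1 alone sets the order, so every 0h sample is a post-dose sample.** The table rows, their footnotes and, for Cycle 1 Day 1, Section 7.1 also set an order.
- **That the pre-dose ECGs and the QTc baseline are lost too.** A reader might infer this from "All ECGs should be performed within 15 minutes prior to the collection of PK sample". But 6.1.1 speaks only of blood draws. Tables 7-5 and 7-6 set pre-dose ECG timing in their own right, and "Baseline is defined as the pre-dose assessment on Cycle 1 Day 1 before study drug administration". The rule in SAP Section 4.7.2 that "If a scheduled pre-dose measurement actually occurred post-dose, then the corresponding measurement will be treated and analyzed similar to an unscheduled post-dose measurement" is a safeguard for stray cases, not evidence of a defect.
- **That the trough error can be stated as a multiple.** The documents give no delay between dose and a mistimed draw, so any multiple rests on an assumed one. The half-life range of 3.5 to 6.3 h comes from another study. Under simple one-compartment decay with 12-hourly dosing, accumulation is 1/(1 − 2^(−12/t½)). This gives 1.10 at 3.5 h and 1.36 at 6.3 h, against the 1.4 that Section 1.2.1.2.4 reports for this study. The short half-life, which would drive a large multiple, fits poorly.

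**Conclusion.** The contradiction is real and explicit, and it cannot be avoided on Cycle 3 Day 1. Its reach is the two trough samples per patient: 2 of 15 on the full schedule and 2 of 5 on the sparse one. The direction of any error is an overstated trough. Its size cannot be given from the documents, and whether any sample was mistimed depends on whether a site followed 6.1.1 over the tables.

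The point is minor. No primary or key secondary result, sample size or error rate depends on it, the ECG baseline is set elsewhere, and the current SAP plans no PK analysis. It still matters for the protocol's PK objective, because Section 1.2.1.2.4 already reports PK results from this study. The conclusion assumes that the footnoted samples are intended as troughs, as their label and footnote indicate.

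**What to change.** Reconcile Section 6.1.1 with Tables 7-7 and 7-8 so that the protocol states one order of pre-dose sample, on-site dose and post-dose samples for each PK day, including Cycle 3 Day 1. This takes one sentence, and no sample or dose is added.

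A wording change cannot recover samples already taken. The SAP times the planned report at last patient last visit, and scheduled PK sampling ends at Cycle 3 Day 1. The sponsor should therefore also compare recorded dose and draw times for every sample labelled pre-dose, flag any drawn after that morning's dose, and state how flagged samples are handled wherever troughs, interval exposure or accumulation from this study are reported. The times are already collected, so the cost is one data check.

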**Table 6-1 Dose and treatment schedule**

Study treatments	Pharmaceutical form and route of administration	Dose	Frequency and/or Regimen
INC280	Tablet for oral use	400 mg (4 x 100 mg or 2 x 200 mg, if available, or 2 x 150 mg + 1 x 100 mg, if applicable)	Twice Daily (BID)

### **6.1.2 Ancillary treatments**

Not applicable.

### **6.1.3 Rescue medication**

Not applicable.

### **6.1.4 Guidelines for continuation of treatment**

For guidelines for dose modification of treatment, refer to [Section 6.3](#).

### **6.1.5 Treatment duration**

Patients may be discontinued from treatment with INC280 earlier due to:

- Disease progression according to RECIST 1.1 as determined by investigator and confirmed by BIRC. Patients may continue treatment with INC280 beyond RECIST 1.1-defined PD (as determined by investigator and confirmed by BIRC) if, in the judgment of the investigator, there is evidence of clinical benefit and the patient wishes to continue on the study treatment.
- Unacceptable toxicity that precludes further treatment
- Discontinued treatment at the discretion of the investigator or the patient
- Death
- Patient is lost to follow-up

## **6.2 Dose escalation guidelines**

Not Applicable.

## **6.3 Dose modifications**

### **6.3.1 Dose modification and dose delay**

For patients who do not tolerate the protocol-specified dosing schedule, dose adjustments are permitted in order to allow the patient to continue the study treatment. All dose modifications, interruptions or discontinuations must be based on the worst preceding toxicity as graded by the NCI Clinical Toxicity Criteria (NCI-CTCAE version 4.03). Any changes must be recorded on the Dosage Administration Record eCRF page.

General guidelines for dose modifications are presented in [Table 6-3](#).

Unless otherwise indicated in [Table 6-3](#), for grade 1 and tolerable grade 2 treatment-related toxicities, patients may continue full doses of study treatment. For intolerable grade 2 or grade 3 treatment-related toxicities, dosing should be interrupted until at least resolution to grade 1 followed by either dose reduction or re-initiation at the same dose level, depending on the type of toxicity as described in [Table 6-3](#). For any grade 4 toxicity, patients should interrupt study treatment until resolution to grade 1, followed by either dose reduction or treatment discontinuation (refer to [Table 6-3](#)).

Any planned variance from the guidelines in [Table 6-3](#), in view of patient safety (unless there is an urgent need for action) when in the opinion of the investigator the patient continues to experience clinical benefit, must first be discussed and approved by the Novartis Medical Lead or designee.

A patient must discontinue treatment with INC280 if, after treatment is resumed at the lowest allowed dose (200 mg BID), the toxicity recurs with the same or worse severity despite use of maximal preventive measures as per the institution guidelines for toxicity prevention and management. All interruptions or change to study drug administration must be recorded on the Dose Administration Record eCRF page.

### **6.3.2 Dose reduction and re-escalation**

An INC280 dose reduction will follow the dose reduction steps described in [Table 6-2](#). For each patient, a maximum of 2 dose level modifications is allowed after which the patient must be discontinued from treatment with INC280. The lowest dose allowed, 200 mg BID in tablets is expected to be pharmacologically active, as the observed steady state plasma trough concentrations ([\[CINC280X1101\]](#), [\[CINC280X2202\]](#), n=6) were above the concentration associated with full cMET inhibition in xenograft mice models (IC90, 120 nM total concentration).

Dose re-escalation of study treatment to the previous dose level is allowed only once, and if no AE leading to dose modification is observed after at least 1 cycle (3 weeks) of study treatment at the reduced dose.

**Table 6-2 Dose reduction steps for INC280**

**INC280 dose levels\***

	Starting dose level - 0	Dose level - 1	Dose level - 2
INC280	400 mg BID	300 mg BID	200 mg BID

\*Dose reduction should be based on the worst toxicity demonstrated at the last dose.

\*\*Dose reduction below 200 mg is not allowed.

**Table 6-3 Criteria for interruption and re-initiation of INC280 treatment**

To be considered recommended dose modifications, unless otherwise specified as mandatory in this [Table 6-3](#). Refer to [Table 6-4](#) for follow-up evaluations as applicable.

Refer to [Table 6-4](#) for follow-up evaluations as applicable.

Recommended dose modifications for INC280	
Worst toxicity CTCAE Grade a	During a cycle of therapy
No toxicity	Maintain dose level
HEMATOLOGICAL	
Neutrophil count decreased (ANC) Neutropenia	
Grade 1 (ANC < LLN - 1500/mm  ; < LLN - 1.5 x 10  /L)	Maintain dose level
Grade 2 (ANC < 1500 - 1000/mm  ; < 1.5 - 1.0 x 10  /L)	Maintain dose level
Grade 3 (ANC < 1000 - 500/mm  ; < 1.0 - 0.5 x 10  /L)	Omit dose until resolved to ≤ grade 2, then: If resolved in ≤ 7 days, resume treatment at the same dose level If resolved in > 7 days, then ↓ 1 dose level
Grade 4 (ANC < 500/mm  ; < 0.5 x 10  /L)	Omit dose until resolved to ≤ grade 2 and then ↓ 1 dose level
Platelet count decreased (Thrombocytopenia)	
Grade 1 (PLT < LLN - 75,000/mm  ; < LLN - 75 x 10  /L)	Maintain dose level
Grade 2 (PLT < 75,000 - 50,000/mm  ; < 75 - 50 x 10  /L)	Maintain dose level
Grade 3 (PLT < 50,000 - 25,000/mm  ; < 50 - 25 x 10  /L)	Omit dose until resolved to ≤ grade 2, then: If resolved in ≤ 7 days, then maintain dose level If resolved in > 7 days, then ↓ 1 dose level
Grade 4 (PLT < 25,000/mm  ; < 25 x 10  /L)	Omit dose until resolved to ≤ grade 2, then ↓ 1 dose level
Febrile neutropenia (ANC < 1000/mm  (< 1.0 x 10  /L), fever > 38.3°C)	Omit dose, then: If resolved in ≤ 7 days, resume treatment at ↓ 1 dose level Mandatory: If resolved in > 7 days, discontinue patient from study drug treatment

Recommended dose modifications for INC280	
Worst toxicity CTCAE Grade a	During a cycle of therapy
Hemoglobin decreased (Anemia)	
Grade 1 (Hgb < LLN - 10.0 g/dL; < LLN - 6.2 mmol/L; < LLN - 100 g/L)	Maintain dose level
Grade 2 (Hgb < 10.0 - 8.0 g/dL; < 6.2 – 4.9 mmol/L; < 100 - 80 g/L)	Maintain dose level
Grade 3 (Hgb < 8.0 g/dL; < 4.9 mmol/L; < 80 g/L)	Omit dose until resolved to ≤ grade 2, then: If resolved in ≤ 7 days, resume treatment at the same dose level If resolved in > 7 days, then ↓ 1 dose level
Grade 4	Omit dose until resolved to ≤ grade 2 and then ↓ 1 dose level Mandatory: If toxicity recurs, discontinue patient from study drug treatment.
RENAL	
Serum creatinine	
Grade 1 (> ULN - 1.5 x ULN)	Maintain dose level
Grade 2 (> 1.5 - 3.0 x ULN)	Omit dose until resolved to ≤ grade 1 or baseline, then resume treatment at the same dose level.
Grade 3 (> 3.0 - 6.0 x ULN)	Omit dose until resolved to ≤ grade 1 or baseline, then resume treatment at ↓ 1 dose level.
Grade 4 (> 6.0 x ULN)	Mandatory: Permanently discontinue patient from study drug treatment
HEPATIC	
Isolated Total Bilirubin elevation*	
Grade 1 (> ULN - 1.5 x ULN)	Maintain dose level
Grade 2 (> 1.5 - 3.0 x ULN)	Omit dose until resolved to ≤ grade 1, then If resolved in ≤ 7 days, maintain dose level If resolved in > 7 days, ↓ 1 dose level
Grade 3 (> 3.0 - 10.0 x ULN)	Omit dose until resolved to ≤ grade 1, then If resolved in ≤ 7 days, ↓ 1 dose level If resolved in > 7 days, discontinue INC280 permanently
Grade 4 (> 10.0 x ULN)	Mandatory: Permanently discontinue patient from study drug treatment
Isolated AST or ALT elevation	
Grade 1 (> ULN - 3 x ULN)	Maintain dose level
Grade 2 (> 3.0 - 5.0 x ULN)	Maintain dose level
Grade 3 (> 5.0 - 20.0 x ULN)	Omit dose until resolved to ≤ grade 1 (or ≤ grade 2 if grade 2 elevation at baseline) then

Recommended dose modifications for INC280	
Worst toxicity CTCAE Grade a	
During a cycle of therapy
 
If resolved in <math>\leq</math> 7 days, then resume treatment at the same dose level If resolved in <math>></math> 7 days, resume treatment at <math>\downarrow</math> 1 dose level

Grade 4 ( $> 20.0 \times$ ULN)	
For patients with clinical benefit from INC280 upon investigator's judgement:
 
 
Omit dose until resolved to <math>\leq</math> grade 1 (or <math>\leq</math> grade 2 if grade 2 elevation at baseline), then resume treatment at <math>\downarrow</math> 1 dose level. Only 1 dose reduction is allowed; if this AE reoccurs at Grade 3 or above, discontinue INC280 permanently.
 
 
For all other patients:
 
 
Mandatory: Permanently discontinue patient from study drug treatment
 

Combined elevations of AST or ALT and Total Bilirubinb,d	

For patients with normal baseline ALT and AST and total bilirubin value:
 
AST or ALT <math>> 3.0 \times</math> ULN combined with total bilirubin <math>> 2.0 \times</math> ULN without evidence of cholestasisc
 
OR
 
For patients with elevated baseline AST or ALT or total bilirubin value:
 
[AST or ALT <math>> 2 \times</math> baseline AND <math>> 3.0 \times</math> ULN] OR [AST or ALT <math>> 8.0 \times</math> ULN], whichever is lower, combined with [total bilirubin <math>> 2 \times</math> baseline AND <math>> 2.0 \times</math> ULN]
	Mandatory: Permanently discontinue patient from study drug treatment
METABOLIC	
Asymptomatic amylase and/or lipase elevation (If symptomatic elevations of any grade, discontinue INC280 permanently)	
Grade 1 ( $>$ ULN - $1.5 \times$ ULN)	Maintain dose level
Grade 2 ( $> 1.5 - 2.0 \times$ ULN)	Maintain dose level
Grade 3 ( $> 2.0 - 5.0 \times$ ULN)	Omit the dose until resolved to $\leq$ grade 2, then If resolved in $\leq$ 14 days, resume treatment at the same dose level If resolved in $>$ 14 days, then $\downarrow$ 1 dose level
Grade 4 ( $> 5.0 \times$ ULN)	Mandatory: Permanently discontinue patient from study drug treatment

Recommended dose modifications for INC280	
Worst toxicity CTCAE Grade a	During a cycle of therapy
CARDIAC	
Electrocardiogram QT corrected (QTc) interval prolonged	
Grade 1 (QTcF 450-480 ms) and Grade 2 (QTcF 481-500 ms) Grade 3 (QTcF $\geq$ 501 ms on at least two separate ECGs)	Maintain dose level  Omit dose until resolved to $\leq$ grade 2, then: If resolved in $\leq$ 7 days, resume treatment at the same dose level If resolved in $>$ 7 days, then $\downarrow$ 1 dose level Mandatory: Permanently discontinue patient from study drug treatment
Grade 4 (QTcF $\geq$ 501 or $>$ 60 ms change from baseline and Torsades de pointes or polymorphic ventricular tachycardia or signs/symptoms of serious arrhythmia)	
GASTROINTESTINAL	
Pancreatitis Grade 2 Grade $\geq$ 3	Maintain dose level Mandatory: Permanently discontinue patient from study drug treatment
Diarrhea** Grade 1 (despite maximal anti-diarrheal medication) Grade 2 (despite maximal anti-diarrheal medication)	Maintain dose level Omit dose until resolved to $\leq$ grade 1, then maintain dose level. If diarrhea returns as $\geq$ grade 2, then omit dose until resolved to $\leq$ grade 1, then resume treatment at $\downarrow$ 1 dose level
Grade 3 or 4 (despite maximal anti-diarrheal medication)	Omit dose until resolved to $\leq$ grade 1, then resume treatment at $\downarrow$ 1 dose level
Vomiting Grade 1 (despite appropriate anti-emetics) Grade 2 (despite appropriate anti-emetics)	Maintain dose level Omit dose until resolved to $\leq$ grade 1, then maintain dose level. If vomiting returns as $\geq$ grade 2, then omit dose until resolved to $\leq$ grade 1, then $\downarrow$ 1 dose level.
Grade 3 (despite appropriate anti-emetics) Grade 4 (despite appropriate anti-emetics)	Omit dose until resolved to $\leq$ grade 2, then $\downarrow$ 1 dose level Omit dose until resolved to $\leq$ grade 2, then $\downarrow$ 1 dose level
Nausea Grade 1 or 2 (despite appropriate anti-emetics) Grade 3 (despite appropriate anti-emetics)	Maintain dose level Omit dose until resolved to $\leq$ grade 1, then $\downarrow$ 1 dose level

Recommended dose modifications for INC280	
Worst toxicity CTCAE Grade a	During a cycle of therapy
SKIN AND SUBCUTANEOUS TISSUE DISORDERS	
Rash/photosensitivity***	
Grade 1	Maintain dose level.
Grade 2	Maintain dose level.
Grade 3, despite skin toxicity therapy	Omit dose until resolved to grade $\leq$ 1, then: If resolved in $\leq$ 7 days, then $\downarrow$ resume treatment at 1 dose level If resolved in $>$ 7 days (despite appropriate skin toxicity therapy), then discontinue patient from study drug treatment
Grade 4, despite skin toxicity therapy	Mandatory: Omit dose and discontinue patient from study drug treatment
RESPIRATORY DISORDERS	
Interstitial Lung Disease (ILD) /Pneumonitis	
Monitor patients for pulmonary symptoms indicative of ILD/Pneumonitis. In addition, withhold INC280 for acute onset of new or progressive unexplained pulmonary symptoms, such as dyspnea, cough and fever and during diagnostic workup for ILD/Pneumonitis to exclude alternative causes such as, but not limited to infections, lymphangitic carcinomatosis, cardiogenic edema, or pulmonary hemorrhage.	
Grade 1	
Interrupt INC280 during diagnostic workup for ILD/Pneumonitis. Exclude infections and other etiologies.
 
In presence of diagnosis of ILD/Pneumonitis after diagnostic workup, it is mandatory to permanently discontinue INC280.
 
Only in absence of diagnosis of ILD/Pneumonitis, study drug may be restarted at the same dose.
 
If it recurs after restarting of study drug, permanently discontinue INC280.

Grade 2	
Mandatory: Interrupt INC280 dose during diagnostic workup for ILD until improvement to <math>\leq</math> Grade 1. Exclude infections and other etiologies.
 
In presence of diagnosis of ILD/Pneumonitis after diagnostic workup, it is mandatory to permanently discontinue INC280.
 
Only in absence of diagnosis of ILD/Pneumonitis, study drug may be restarted following these guidelines:
 
 
• If resolves to <math>\leq</math> Grade 1 in <math>\leq</math> 7 days reduce study drug by 1 dose level
 
• If fails to resolve to <math>\leq</math> Grade 1 within 7 days or recurs after resumption of study drug at decreased dose, permanently discontinue INC280
 

Grade 3 and Grade 4	Mandatory: Permanently discontinue study drug

Recommended dose modifications for INC280	
Worst toxicity CTCAE Grade a	During a cycle of therapy
	Treat with IV steroids as clinically indicated. Oxygen therapy as indicated.
Fatigue/ Asthenia (General disorders and administration site conditions)	
Grade 1 or 2	Maintain dose level
Grade 3	Omit dose until resolved to ≤ grade 1, then: If resolved in ≤ 7 days, resume treatment at same dose level If resolved in > 7 days, resume treatment at ↓ 1 dose level
Peripheral edema	
Grade 1 or 2	Maintain dose level
Grade 3	Discontinue dose until resolved to ≤ Grade 1, then ↓ 1 dose level
Other adverse events	
Grade 1 or 2	Maintain dose level, consider to initiate appropriate support medication. For any intolerable grade 2 (e.g.: limiting instrumental ADL), consider omitting the dose until resolved to ≤ grade 1, then ↓ 1 dose level.
Grade 3	Omit dose until resolved to ≤ grade 2, then ↓ 1 dose level
Grade 4	Omit dose and then discontinue from study drug treatment
All dose modifications should be based on the worst preceding toxicity. a Common Toxicity Criteria for Adverse Events (CTCAE Version 4.03).	
b "Combined" defined as: total bilirubin increase to the defined threshold concurrently with ALT/AST increase to the defined threshold	
c "Cholestasis" defined as: ALP elevation (> 2.0 x ULN and R value (ALT/ALP in x ULN) < 2.0) in patients without bone metastasis, or elevation of ALP liver fraction in patients with bone metastasis	
d If combined elevations of AST or ALT and total bilirubin do not meet the defined thresholds, please follow the instructions for isolated elevation of total bilirubin and isolated elevation of AST/ALT, and take a conservative action based on the degree of the elevations (e.g. discontinue treatment at the situation when omit dose is needed for one parameter and discontinue treatment is required for another parameter). After all elevations resolve to the defined thresholds that allow treatment re-initiation, restart the treatment either at the same dose or at one dose lower if meeting a criterion for dose reduction	
* Note: If total bilirubin > 3.0 x ULN is due to the indirect (non-conjugated) component only, and hemolysis as the etiology has been ruled out as per institutional guidelines (e.g., review of peripheral blood smear and haptoglobin determination), then ↓ 1 dose level and continue treatment at the discretion of the investigator.	
** Note: antidiarrheal medication is recommended at the first sign of abdominal cramping, loose stools or overt diarrhea	
*** During the whole duration of treatment with INC280, the patient is recommended to use precautionary measures against ultraviolet exposure (e.g., use of sunscreen, protective clothing and avoid sunbathing or using a solarium intensively).	

